#### STUDY PROTOCOL

#### **METHODS**

## Study design and setting

We will perform a prospective, randomized controlled trial comparing i-scan 1 (surface enhancement with contrast enhancement) with conventional HDWL during colonoscopy for the detection of colorectal neoplasia; a representative example of endoscopic images using i-scan 1 and HDWL is shown in Figure 1. The study will be conducted at the University of California, San Francisco (UCSF), an academic, tertiary care medical center serving over 1.2 million patients annually in the San Francisco Bay Area.

# **Study eligibility**

Patients will be recruited between February 1, 2017 and December 31, 2017. Inclusion criteria included patients ages 50 to 75 years who were scheduled for outpatient colonoscopy for the indications of CRC screening, post-polypectomy surveillance, or diagnostic workup for a positive fecal-based test (FIT). Exclusion criteria were inpatients and patients with inflammatory bowel disease, colorectal cancer, polyposis syndromes, previous surgical resection of any portion of the colon or rectum, and patients referred for endoscopic mucosal resection of previously diagnosed colorectal polyps.

#### Randomization

Patients will be randomized (1:1) to HDWL alone or i-scan 1 during colonoscopy. The randomization order will be determined by using a computer-generated sequence in block sizes of 30. Sealed, opaque envelopes containing the randomization assignment will be prepared by one investigator. After obtaining informed consent from the patient, the envelope will be opened to reveal the randomization assignment prior to beginning the procedure.

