### Colonoscopy procedure

All patients will need to complete a bowel preparation using split-dose US Food and Drug Administration-approved preparations. Four attending physicians, each of whom performed over 500 colonoscopies the year prior, will perform withdrawal in every procedure. Insertion of the colonoscope and withdrawal from cecum will be performed with the assigned imaging modality (i.e., HDWL or i-scan 1). The i-scan 1 setting that will be used will be the "out of the box" setting (supplementary table) that is standard with Pentax colonoscopes (Pentax EC-3890 and EC-3490); no adjustments will be made to the setting. If a lesion/polyp were detected, the physician will be permitted to change from i-scan 1 to HDWL and vice versa at their discretion to interrogate and better characterize the lesion/polyp per their routine practice. Once the lesion/polyp is removed and retrieved, the physician can return to the assigned imaging modality for inspection. Withdrawal time will be measured from the time withdrawal from the cecum began to the end of the examination – the time will not be "paused" for polyp resection. Withdrawal time during a negative colonoscopy exam (one in which no polyps were identified and no interventions were performed), called the "negative withdrawal time," will also be separately analyzed. Resected polyps will be sent for pathologic examination as part of routine clinical care.

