#### **Outcome measurement**

The primary outcome measured will be the ADR, defined as the proportion of subjects with at least one traditional adenoma (including tubular or villous adenomas, and adenomas with high grade dysplasia or adenocarcinoma) of any size. Secondary outcomes measured included the adenomas per colonoscopy (APC), serrated adenoma detection rate (SDR), defined as the proportion of subjects with at least one serrated polyp (serrated adenoma or traditional serrated

adenoma) of any size as well as the neoplasia detection rate (NDR), defined as the percentage of colonoscopies in which at least one traditional adenoma or serrated adenoma was found. Additionally, the location, size, morphology and number of polyps will also be recorded. Flat polyps will be defined as flat appearing polyps, in which the height was less than two times the diameter. Histology of polyps will be evaluated by expert gastrointestinal pathologists at UCSF, who will be blinded to the specific endoscopic diagnosis and the histopathological diagnosis was used as the gold-standard. High risk adenomas will be defined as an adenoma of any size with high grade dysplasia or a villous component, an adenoma greater than ten millimeters in size, adenocarcinoma, and, or three or more adenomas of any size found on a single colonoscopy.

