# Sample size and statistical analysis

The sample size calculation for the primary outcome of ADR was based on the average ADR of our group over the previous two years of 30%, which we estimated would be the control (HDWL) group's ADR. We estimated a 10% difference between groups based on a previous study. To achieve an absolute difference of 10% in the ADR between groups with a statistical type I error of 5% (two-sided) and power of 80%, a minimum of 356 patients per group was needed (712 patients total). Adjusting for a 4% drop-out due to bowel prep or inability to intubate the cecum, we targeted enrollment of 740 patients.

Intention-to-treat analysis will be used to assess the primary and secondary outcomes. We will also perform per-protocol analyses to explore differences in the primary and secondary outcomes after excluding patients with preparations that were considered too difficult to correct with intraprocedural washing (i.e., Boston bowel prep score < 2 in any segment). Only patients with a complete procedure and adequate bowel preparation will be included in the per-protocol analyses. Categorical data will be compared by the  $\chi^2$ -test or Fisher Exact test where appropriate

and numerical data will be compared by the Student's t-test. Statistical significance will be defined as a two-sided p-value < 0.05.

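### A single fixed block size of 30, in a trial whose endoscopists know each assignment, lets about 6% of allocations be deduced in advance; large, varied, undisclosed blocks would nearly remove this at little cost.

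*Combined protocol and SAP*

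**What the plan says.** All the allocation rules are in the Randomization section of the combined protocol and SAP:

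- **Ratio:** "Patients will be randomized (1:1) to HDWL alone or i-scan 1 during colonoscopy".
- **Sequence:** a "computer-generated sequence in block sizes of 30". No second size and no stratification factor is given, and nothing says that the size is withheld from staff.
- **Envelopes:** "Sealed, opaque envelopes containing the randomization assignment will be prepared by one investigator". Numbering is not mentioned. The section does not say who enrols patients, or whether the preparing investigator consents patients or performs colonoscopy.
- **Reveal:** "After obtaining informed consent from the patient, the envelope will be opened to reveal the randomization assignment prior to beginning the procedure".

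The Colonoscopy procedure section adds that "Four attending physicians, each of whom performed over 500 colonoscopies the year prior, will perform withdrawal in every procedure", and that insertion and withdrawal both use the assigned mode. The operator therefore knows the arm. The only blinding described, under Outcome measurement, is of the pathologists, "who will be blinded to the specific endoscopic diagnosis".

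**The concern.** With a fixed, known block size, the assignments already opened carry information about those still sealed. Once 15 patients in a block have gone to one arm, every remaining patient in that block must go to the other. Opaque envelopes hide the contents of the next envelope, but not what follows from the previous ones.

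The setting makes a running count feasible. There is one site, there are four operators, and each operator sees the arm used. Recruitment is planned from 1 February to 31 December 2017, which is 334 days for 740/30 = 24.7 blocks, or about 13.5 days per block.

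What is at stake is the comparability of the arms. The eligibility section mixes screening, post-polypectomy surveillance and positive-FIT patients, who may well differ in expected ADR. If a recruiter knows the next arm, the choice of whom to approach could shift the case mix between arms. The planned primary comparison is an unadjusted chi-square or Fisher test, so such a shift would pass into the result.

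**Working it through.** **The plan's own figure.** Inputs from the sample size section: 30% versus 40%, two-sided 5%, 80% power. With pooled variance and no continuity correction, n per arm = [1.960 × √(2 × 0.35 × 0.65) + 0.8416 × √(0.30 × 0.70 + 0.40 × 0.60)]² / 0.10² = (1.3221 + 0.5646)² / 0.01 = 356. This matches the stated 356 per arm and 712 in total. Nothing below changes it. The documents give no figure for predictability, so that is computed here.

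**Certain allocations, fixed block of 30.** For a block of 2m with m per arm, the expected number left once one arm is full is 2m/(m + 1).

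- m = 15: 30/16 = 1.875 per block, or 1.875/30 = 6.25%.
- 740 patients make 24 full blocks plus 20 patients. The full blocks give 24 × 1.875 = 45, and the part block adds almost nothing.
- Simulation of 740 patients: mean 44.9, 95% range 34 to 57, or 6.1% of patients.

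This requires knowing the block size and block boundaries and having every earlier assignment in the block.

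**Bias from acting on certain allocations.** Suppose high-ADR patients are always placed in one arm and low-ADR patients in the other. The bias is then the share of certain allocations × the ADR gap. The documents give no gap by patient type; 10 to 20 points is an assumption.

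- 45/740 = 6.1%; 6.1% × 10 = 0.6 points; 6.1% × 20 = 1.2 points.
- With 30% ADR in both arms, the standard error at 356 per arm is √(2 × 0.30 × 0.70/356) = 3.43 points. The bias is therefore about 0.18 to 0.35 standard errors.

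**Best-guess prediction.** Always guessing the arm with more places left succeeds in [m + 2^(2m−1)/C(2m, m) − 1/2]/(2m) of allocations. For m = 15 this is 59.9%, or 59.7% in simulation over 740 patients.

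**Alternatives.** For the varied sizes, the guesser is assumed to know the set of sizes but not their order.

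| Scheme | Certain in advance | Best-guess success |
|---|---|---|
| Fixed 30 (plan) | about 6% | 59.9% |
| Random 20, 30, 40 | about 1.0% | 59.7% |
| Five random sizes from 20 to 40 | about 0.1% | about 59.7% |
| Random 10, 20, 30 | 1.7% | 61.3% |
| Random 4, 6, 8 | 2.1% | 68.1% |
| Fixed 4 | 33% | 70.8% |
| Simple randomization | 0% | 50% |

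Varying large blocks removes most of the certainty but does not reduce guessing. Small blocks make guessing easier, even when their sizes vary.

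**What blocking buys.** Arm totals within a block of 30 can differ by at most 15, and at exactly 740 by at most 10 (15 versus 5 in the last 20 patients). Under simple randomization the difference averages 22, with a 95th percentile of 54. At a difference of 54 among 712 analysed, power falls only from 80.0% to 79.7%.

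**The case against.** The strongest reply is that a block of 30 is already large and the plan has real concealment measures: computer generation, sealed opaque envelopes and a reveal only after consent. Deduction needs someone to know the block size and pool counts across four endoscopists, and no shared allocation log is described. Patients are already scheduled for colonoscopy, which limits freedom to choose one type on demand. All of this stands, and it is why the bias figures are ceilings. It does not remove the deduction, because the block size is written in the protocol and the envelopes do not conceal past assignments.

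Four stronger readings are tempting, and none is supported:

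- **That the preparing investigator recruits and could know every allocation.** The protocol states neither overlap nor separation. Silence justifies asking for a statement, not asserting a flaw.
- **That the block brings no benefit.** Blocking limits arm imbalance and keeps the arms balanced over the recruitment period. The gain is small at 740, but it is a gain.
- **That no later analysis could correct the damage.** Indication is known at eligibility, so an imbalance on it could be tabulated and adjusted for. Only steering on unrecorded factors would escape, although no adjustment is planned at present.
- **That the larger bias from acting on every best guess justifies varying the blocks.** With the same assumed gap, that worst case is about (2 × 0.599 − 1) = 0.198 × 10 to 20 points, or roughly 2.0 to 3.9 points. Varied large blocks leave guess success near 60%, so they do not address it.

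**Conclusion.** The concern holds in a limited form. With one fixed block of 30 and operators who know each assignment, about 6% of allocations (about 45 of 740) can be known with certainty by someone who knows the block size and pools the full tally. With an assumed 10 to 20 point ADR gap between patient types and perfect steering, the ADR difference could be biased by at most about 0.6 to 1.2 points, against the planned 10. This is a conditional ceiling; the documents contain no sign that anyone would track or exploit the sequence. The sample size calculation is unaffected. The missing statement on the list-holder's independence is, by itself, a reporting gap. The change is worth making because it improves a stated rule at almost no cost.

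**What to change.** 1. Replace the fixed block of 30 with randomly ordered, still large block sizes, for example several even sizes from 20 to 40. Remove the sizes from any document available to endoscopists or recruiting staff. Certain allocations fall from about 6% to about 1% or less; best-guess success stays near 60%. Do not move to small blocks.
2. Have the list and consecutively numbered envelopes prepared and held by an existing staff member who neither consents patients nor performs colonoscopy, and say so in the Randomization section.

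**Cost:** a few sentences, a regenerated list, and a slightly larger possible end-of-trial imbalance (up to 20 if recruitment stops inside a block of 40, against 15 inside a block of 30). Sample size is unchanged. If enrolment is already under way or complete, the sponsor can still record who generated and held the list and whether that person recruited patients or performed procedures.

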### Colonoscopy procedure

All patients will need to complete a bowel preparation using split-dose US Food and Drug Administration-approved preparations. Four attending physicians, each of whom performed over 500 colonoscopies the year prior, will perform withdrawal in every procedure. Insertion of the colonoscope and withdrawal from cecum will be performed with the assigned imaging modality (i.e., HDWL or i-scan 1). The i-scan 1 setting that will be used will be the "out of the box" setting (supplementary table) that is standard with Pentax colonoscopes (Pentax EC-3890 and EC-3490); no adjustments will be made to the setting. If a lesion/polyp were detected, the physician will be permitted to change from i-scan 1 to HDWL and vice versa at their discretion to interrogate and better characterize the lesion/polyp per their routine practice. Once the lesion/polyp is removed and retrieved, the physician can return to the assigned imaging modality for inspection. Withdrawal time will be measured from the time withdrawal from the cecum began to the end of the examination – the time will not be "paused" for polyp resection. Withdrawal time during a negative colonoscopy exam (one in which no polyps were identified and no interventions were performed), called the "negative withdrawal time," will also be separately analyzed. Resected polyps will be sent for pathologic examination as part of routine clinical care.

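### Does the permissive wording on returning to the assigned imaging mode after a lesion undermine the comparison of i-scan 1 with HDWL?

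*Combined protocol and SAP*

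**What the plan says.** Four places in the combined protocol and SAP bear on this.

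- **Randomization** names the arms: "Patients will be randomized (1:1) to HDWL alone or i-scan 1 during colonoscopy".
- **Colonoscopy procedure** sets the general rule: "Insertion of the colonoscope and withdrawal from cecum will be performed with the assigned imaging modality". It then lets the physician change mode in either direction once a lesion is found, for the stated purpose of examining and characterising that lesion. It closes with: "Once the lesion/polyp is removed and retrieved, the physician can return to the assigned imaging modality for inspection".
- **Outcome measurement** makes ADR the primary outcome, "defined as the proportion of subjects with at least one traditional adenoma", and APC a secondary outcome. On lesion data it says: "Additionally, the location, size, morphology and number of polyps will also be recorded".
- **Sample size and statistical analysis** specifies intention-to-treat (ITT) analysis of the primary and secondary outcomes. It also plans a per-protocol analysis restricted to complete procedures with adequate preparation. Neither analysis refers to the imaging mode actually used.

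**The concern.** The imaging mode during inspection is the only thing randomized, and the permitted switch is into the comparator's mode. A sentence saying the physician *can* go back, rather than *will*, seems to leave this to discretion. If some physicians stayed in the other mode after the first lesion, later lesions would be found under the wrong arm's technique and the arms would move closer together.

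APC is more exposed because it counts every adenoma, including those found after a switch. ADR is less exposed. It is settled by the first traditional adenoma, so drift matters only when every lesion up to the switch was something else. With the mode at first sighting not listed as recorded, a reader faced with a small APC difference might be unable to tell a weak technology from mode drift.

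**Working it through.** **1. The plan's own figure.** Inputs from Sample size and statistical analysis: control ADR, "average ADR of our group over the previous two years of 30" percent; effect, "To achieve an absolute difference of 10% in the ADR between groups"; error rates, "statistical type I error of 5% (two-sided) and power of 80" percent. With pooled variance and no continuity correction:

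n = [1.960·√(2·0.35·0.65) + 0.842·√(0.30·0.70 + 0.40·0.60)]² / 0.10² = (1.322 + 0.565)² / 0.01 ≈ 356 per arm.

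This matches the plan, and power at 356 per arm is 80.0%.

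**2. The text read as a whole.** The general rule covers insertion and the whole withdrawal. The exception starts when a lesion is detected and serves only to characterise it. Once the lesion is removed and retrieved, that purpose is spent and the general rule applies again. The disputed sentence itself ties the assigned mode to inspection. Its verb most naturally marks *when* the physician may go back, not *whether*.

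**3. What drift would cost if it happened.** The documents give no non-return rate, lesion dispersion or polyp mix, so all of these are assumptions:

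- Detected adenomas are gamma-Poisson with shape k = 0.4, 0.7 or 1.5. The mean μ solves 1 − (1 + μ/k)^(−k) = 0.30 (HDWL) or 0.40 (i-scan).
- A share π = 30% or 50% of polyps are non-adenomatous, so their mean is h = μπ/(1 − π).
- A fraction f of patients in both arms stay in the other mode for the rest of the examination after the first detected polyp.

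Let μ be the assigned mode's mean, μₒ the other mode's, r = μ + h and s(t) = rt + μₒ(1 − t), with t the position along withdrawal. With full non-return,

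P(no adenoma) = (1 + r/k)^(−k) + ∫₀¹ h(1 + s(t)/k)^(−k−1) dt.

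Because f is a patient-level fraction, ADR(f) = (1 − f)·ADR + f·ADR(full non-return).

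Worked cell, k = 0.7 and π = 50%: ADR with full non-return is 32.5% (HDWL) and 37.0% (i-scan). At f = 10%:

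- HDWL: 0.9·30 + 0.1·32.5 = 30.25%
- i-scan: 0.9·40 + 0.1·37.0 = 39.70%
- Difference: 9.45 points
- Power: Φ[(0.0945·√356 − 1.960·0.6744)/0.6711] = Φ(0.687) ≈ 75%

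Over all six combinations of k and π:

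| f, both arms | ADR difference (points) | Power | APC difference reduced by |
|---|---|---|---|
| 0% | 10.0 | 80.0% | 0% |
| 2% | 9.9 | 79-80% | 2-3% |
| 5% | 9.7-9.9 | 78-79% | 4-7% |
| 10% | 9.4-9.8 | 75-78% | 8-14% |
| 25% | 8.5-9.4 | 66-75% | 19-35% |
| 50% | 7.0-8.8 | 50-70% | 38-69% |

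If only the i-scan arm drifts, f = 10% gives 9.7-9.9 points and 77-79% power. Under these assumptions, 65-90% of adenoma-positive patients have an adenoma as their first lesion, so their ADR status is fixed before any switch is allowed.

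**4. Sensitivity to the model.** The table holds π equal in both arms, which implies that i-scan also finds more non-adenomas. Holding the non-adenoma rate equal instead gives smaller losses. In the worst cell (k = 0.4, π = 50%), f = 10% gives 9.5 points and 76% power rather than 9.4 and 75%; f = 50% gives 7.5 and 56% rather than 7.0 and 50%.

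**5. Direction.** If the two modes detect equally well, switching between them changes nothing, so the type I error is untouched.

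**The case for a change.** The best case for a change is that the rule restoring the randomized technique should not be permissive, that the plan has 80.0% power with nothing to spare, and that mode at first sighting cannot be reliably recovered afterwards. The remedy would be one sentence and one field per lesion.

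Part of this stands. A mandatory verb would be clearer. A descriptive count by arm of lesions first seen in the other mode would help in reading a small APC difference. The mechanism is sound, and APC is the more exposed outcome.

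The rest is weaker. The argument takes one verb out of a paragraph whose other sentences settle the matter. The documents show that mode is not *listed* among the polyp descriptors. They do not show that it goes uncaptured, since that list does not claim to be the whole data form. The 25% and 50% rows are extremes: they need routine departure from the stated withdrawal rule, lasting from the first polyp to the end, and nothing in the documents suggests this.

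A recorded mode would also not lead to a better analysis. ITT would remain primary. A mode-adherence criterion in the per-protocol set would do harm, because only patients with a detected lesion can fail it, and it would therefore select on the outcome. With drift in the i-scan arm only (k = 0.7, π = 50%), excluding non-returners turns an ITT difference of 9.2 points into 4.8 at f = 25%, and 8.5 into −2.4 at f = 50%.

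**Conclusion.** No change follows. The section as a whole already requires inspection in the assigned mode, and an investigator who follows it gets the intended comparison. What remains is a loose verb and a descriptive data item that is not listed. Correcting either would leave the 356 per arm, the tests, the analysis sets and the conclusions as they are.

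If some drift did occur, the primary outcome would lose little. Up to 10% non-return in both arms costs at most about 5 points of power (80.0% to 75%) and 0.6 points of the 10-point ADR difference. APC, a secondary outcome, would lose up to 14% of its difference. In the range examined, the error shrinks a true effect and does not produce a false claim.

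These sizes rest on assumed non-return rates, dispersion and polyp mix, because the documents supply none of them. The conclusion would change only if the documents showed that physicians were meant to finish examinations in the other mode, and they do not.

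### Does the lack of a resection-free inspection time in exams with a polyp weaken the comparison of adenoma detection?

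*Combined protocol and SAP*

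**What the plan says.** The Colonoscopy procedure section plans two time measures. For every exam, "Withdrawal time will be measured from the time withdrawal from the cecum began to the end of the examination", and the section states openly that the clock is not stopped for polyp resection. The second measure, to be analysed separately, is "Withdrawal time during a negative colonoscopy exam (one in which no polyps were identified and no interventions were performed". The same section allows lesion work-up to involve a change of imaging: "the physician will be permitted to change from i-scan 1 to HDWL and vice versa at their discretion". That time also counts as withdrawal time.

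Under Outcome measurement, ADR (at least one traditional adenoma, yes or no) is primary. On the count outcome the section says "Secondary outcomes measured included the adenomas per colonoscopy (APC"). It adds that "the location, size, morphology and number of polyps will also be recorded". Under Sample size and statistical analysis, the control rate is "the average ADR of our group over the previous two years of 30" percent, the target difference is 10 points and the enrolment target is 740. No analysis in that section adjusts for time.

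**The concern.** The operator cannot be blinded. Under Randomization, "the envelope will be opened to reveal the randomization assignment prior to beginning the procedure". That section does not say who opens the envelope, but the operator then examines with the assigned modality. If physicians look longer in one arm, part of a detection difference could come from effort and not from the image. A reader would want inspection time to check this, and neither measure supplies it for an exam with a polyp:

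- Total time rises with every polyp removed, so the arm that finds more looks slower even when inspection is equal.
- Negative time is defined only where nothing was found. It cannot register extra looking that starts after a first find.
- Negative time would show only part of any extra effort aimed at patients expected to have polyps. The trial mixes risk levels: "CRC screening, post-polypectomy surveillance, or diagnostic workup for a positive fecal-based test (FIT").

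At stake would be the explanation of a positive result, chiefly for APC. Looking on after a first adenoma can add to a count but cannot change a yes/no outcome that is already yes.

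**Working it through.** **1. The plan's own figure.** Two proportions, 30% v 40%, two-sided 5%, power 80%, pooled variance, no continuity correction:

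n = [1.96·√(2·0.35·0.65) + 0.842·√(0.30·0.70 + 0.40·0.60)]² / 0.10² = (1.322 + 0.565)² / 0.01 ≈ 356 per group, as stated. Withdrawal time does not enter. The target of 740 gives 370 per arm.

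**2. How many exams lack a clean time.** Polyp-free exams number at most 370 × 0.70 = 259 (HDWL) and 370 × 0.60 = 222 (i-scan 1), 481 in all. So at least 740 − 481 = 259 (35%) have none. Non-adenomatous polyps also exclude an exam: if 40/50% to 60/70% of exams have any polyp (assumed, HDWL/i-scan 1), the share is 45% to 65%.

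**3. What negative time can still detect.** Difference detectable with 80% power = 2.80 × SD × √(1/n₁ + 1/n₂). The documents give no SD, so 2 to 4 minutes is assumed.

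- 259 and 222 exams: 0.51 min (SD 2), 0.77 (SD 3), 1.02 (SD 4).
- All exams, 370 and 370: 0.41, 0.62, 0.82. The subset is 24% less precise (0.51/0.41).
- If 60/70% of exams have a polyp (148 and 111 exams): 0.70 (SD 2) to 1.41 (SD 4).

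**4. Does restriction to negative exams distort it?** Two simple models of a withdrawal were used, with every input assumed.

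- *Model A:* inspection mean 9, SD 3 min; detection of a lesion 60%, 75% or 85% at 9 min; lesion load gamma-Poisson, doubled in a higher-risk 40% of patients; HDWL ADR 30%. Results are ranges over four settings. Only the three detection levels are specified here, so the ranges are illustrative.
- *Model B:* inspection mean 8, SD 2 min; detection 1 − exp(−0.12 × minutes); gamma-Poisson adenomas (mean 0.8) and other polyps (mean 0.6); HDWL ADR 29.7%, APC 0.485.

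With one arm 1 min slower throughout, negative time shows +1.04 to +1.05 (A) and +1.03 (B). With 2 min it shows +2.07 to +2.09 and +2.04. General pace is measured almost without bias.

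**5. What escapes it.**

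- *Extra looking only after the first find.* Negative time shows 0. Model A, 1 or 2 min per exam with a polyp: ADR +0.2 to +0.7 points, APC +0.013 to +0.040. Model B, pace after the find slowed by 25%, 50% or 100%: ADR +0.3, +0.6 or +0.9 points; APC +0.028, +0.053 or +0.083.
- *Extra looking only in higher-risk patients (Model A).* ADR +0.4 to +1.2 points, but negative time shows 73% to 81% of the time difference. If ADR moves roughly in proportion, the unsignalled part is 0.19 × 0.4 ≈ 0.1 to 0.27 × 1.2 ≈ 0.3 points.

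**6. Scale.** With an APC SD of 0.90 (from Model A), the standard error of the APC difference is 0.90 × √(2/370) = 0.066, and the detectable difference is 2.80 × 0.066 ≈ 0.19. Model A's shifts are 0.013/0.066 ≈ 0.2 to 0.040/0.066 ≈ 0.6 standard errors. Model B's largest is 0.083/0.066 ≈ 1.3, and needs inspection time after the first find to double in one arm only. For ADR, 0.2 to 1.2 points stands against 10.

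**7. Would a net clock settle it?** In Model A the after-find scenario raises true mean inspection by 0.47 to 1.16 min. Even an error-free clock on all 740 exams detects 0.62 min at that model's SD of 3, so the lower part of the range would be missed. At SD 2 (0.41) it would not. Real stop-start timing adds error that no model here includes.

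**The case for a change.** The best case for the concern is factual and largely correct. No planned measure isolates inspection in an exam with a polyp. (A polyp seen but left in place gives a time free of resection, though not of work-up.) Nothing described in the documents would let it be rebuilt afterwards. Adjusting total time for polyp count is possible from recorded data but not planned, and would not resolve the matter. In Model A, extra inspection after a find leaves +0.45 to +1.12 min after adjustment, while equal inspection with 0.25 to 0.5 min more work-up per polyp in one arm leaves +0.21 to +0.63. The ranges overlap. The price looks low: one timing rule and one data field.

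Those facts stand. They do not amount to a fault, for three reasons.

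- **The mechanism is conjecture.** It needs effort that differs by arm and either begins only after a find or goes only to selected patients. Nothing in the documents points to either. Changing modality is allowed for characterising a lesion within routine practice.
- **The remedy meets the same obstacle.** Someone must decide, at each lesion, when work-up ends and inspection resumes. That is the boundary adjusted total time cannot draw. Staff who may know the arm would make the call repeatedly, with error that could differ by arm. The documents do not say who times the exam, so the effort is unknown.
- **The result would alter nothing.** Net time is observed after randomization. It could be described, but it should not enter the primary analysis and could not prove a mechanism.

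**Conclusion.** The concern does not hold. Leaving the clock running is a disclosed design choice, paired with a separate analysis of negative withdrawal time that serves as a check on general pace. The ADR and APC comparisons are protected by randomization, and the sample size and primary test are unaffected. What the planned measures miss is worth at most about 1 point of ADR in the scenarios examined. For APC it is 0.013 to 0.040, or 0.083 under the most extreme assumption, below the 0.19 detectable in every case.

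The count of 259 exams follows from the plan's own rates and is a minimum. The sizes of effect rest on assumed SDs, polyp rates and detection models. Larger SDs or polyp rates would blunt the pace check (up to 1.41 min detectable) but would not touch the validity of the randomized comparison. An extra descriptive time variable is something the investigators may like to have; its absence is not an error.
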